## 7.3 Subject Population(s) for Analysis and Duration of Study

Analysis of both primary and secondary end points will be performed on an intention to treat basis. A maximum of 58 patients will be required if all 3 dose levels are investigated in the Phase I trial. If 1-2 patients are enrolled per month, then we expect up to approximately 5 years will be needed to complete enrollment.

# 8 Safety and Adverse Events

## 8.1 Definitions

### Unanticipated Problems Involving Risk to Subjects or Others

Any incident, experience, or outcome that meets all of the following criteria:

- Unexpected in nature, severity, or frequency (i.e. not described in study-related documents such as the IRB-approved protocol or consent form, the investigators brochure, etc)
- Related or possibly related to participation in the research (i.e. possibly related means there is a reasonable possibility that the incident experience, or outcome may have been caused by the procedures involved in the research)
- Suggests that the research places subjects or others at greater risk of harm (including physical, psychological, economic, or social harm).

### Adverse Event

An **adverse event** (AE) is any symptom, sign, illness or experience that develops or worsens in severity during the course of the study. Intercurrent illnesses or injuries should be regarded as adverse events. Abnormal results of diagnostic procedures are considered to be adverse events if the abnormality:

- results in study withdrawal
- is associated with a serious adverse event
- is associated with clinical signs or symptoms
- leads to additional treatment or to further diagnostic tests
- is considered by the investigator to be of clinical significance

CONFIDENTIAL

### **Serious Adverse Event**

Adverse events are classified as serious or non-serious. A **serious adverse event** is any AE that is:

- fatal
- life-threatening
- requires or prolongs hospital stay
- results in persistent or significant disability or incapacity
- a congenital anomaly or birth defect
- an important medical event

Important medical events are those that may not be immediately life threatening, but are clearly of major clinical significance. They may jeopardize the subject, and may require intervention to prevent one of the other serious outcomes noted above. For example, drug overdose or abuse, a seizure that did not result in in-patient hospitalization, or intensive treatment of bronchospasm in an emergency department would typically be considered serious.

All adverse events that do not meet any of the criteria for serious should be regarded as **non-serious adverse events**.

### **Adverse Event Reporting Period**

The study period during which adverse events must be reported is normally defined as the period from the initiation of any study procedures to the end of the study treatment follow-up. For this study, the study treatment follow-up is defined as 6 months following the last dose of hydroxychloroquine (i.e. approximately 8 months following initial TACE).

### **Preexisting Condition**

A preexisting condition is one that is present at the start of the study. A preexisting condition should be recorded as an adverse event if the frequency, intensity, or the character of the condition worsens during the study period.

### **General Physical Examination Findings**

At screening, any clinically significant abnormality should be recorded as a preexisting condition. At the end of the study, any new clinically significant findings/abnormalities that meet the definition of an adverse event must also be recorded and documented as an adverse event.

### **Post-study Adverse Event**

All unresolved adverse events should be followed by the investigator until the events are resolved, the subject is lost to follow-up, or the adverse event is otherwise explained. At the last scheduled visit, the investigator should instruct each subject to report any subsequent event(s) that the subject, or the subject's personal physician, believes might reasonably be related to participation in this study. The investigator should notify the study sponsor of any death or adverse event occurring at any time after a subject has discontinued or terminated study participation that may reasonably be related to this study. The sponsor should also be notified if the investigator should become aware of the development of cancer or of a congenital anomaly in a subsequently conceived offspring of a subject that has participated in this study.

### **Abnormal Laboratory Values**

A clinical laboratory abnormality should be documented as an adverse event if one or more of the following conditions is met:

- The abnormality suggests a disease and/or organ toxicity
- The abnormality is of a degree that requires active management or treatment; e.g. change of dose, discontinuation of the drug, more frequent follow-up assessments, further diagnostic investigation, etc.

### **Hospitalization, Prolonged Hospitalization or Surgery**

CONFIDENTIAL

Any adverse event that results in hospitalization or prolonged hospitalization should be documented and reported as a serious adverse event unless specifically instructed otherwise in this protocol. Any condition responsible for surgery should be documented as an adverse event if the condition meets the criteria for an adverse event.

Neither the condition, hospitalization, prolonged hospitalization, nor surgery are reported as an adverse event in the following circumstances:

- Hospitalization or prolonged hospitalization for diagnostic or elective surgical procedures for a preexisting condition. Surgery should **not** be reported as an outcome of an adverse event if the purpose of the surgery was elective or diagnostic and the outcome was uneventful.
- Hospitalization or prolonged hospitalization required to allow efficacy measurement for the study.
- Hospitalization or prolonged hospitalization for therapy of the target disease of the study, unless it is a worsening or increase in frequency of hospital admissions as judged by the clinical investigator.

## **8.2 Recording of Adverse Events**

At each contact with the subject, the investigator must seek information on adverse events by specific questioning and, as appropriate, by examination. Information on all adverse events should be recorded immediately in the source document (i.e. PennChart) to a paper AE form which will include event grade, start/stop dates, outcome, PI attribution of relation to study, PI attribution of expectedness and PI signature. Information completed on paper AE forms will then be entered into PennCTMS and the study's eCRF database (REDCap). All clearly related signs, symptoms, and abnormal diagnostic procedure results should be recorded in the source document, though should be grouped under one diagnosis.

All adverse events occurring during the study period (up to 6 months after last dose of HCQ) must be recorded. The clinical course of each event should be followed until resolution, stabilization, or until it has been determined that the study treatment or participation is not the cause. Serious adverse events that are still ongoing at the end of the study period must be followed up to determine the final outcome. Any serious adverse event that occurs after the study period and is considered to be possibly related to the study treatment or study participation should be recorded and reported immediately.

## **8.3 Reporting of Serious Adverse Events and Unanticipated Problems**

Investigators and the sponsor must conform to the adverse event reporting timelines, formats and requirements of the various entities to which they are responsible, but at a minimum those events that must be reported are those that are:

- related to study participation,
- unexpected, and
- serious or involve risks to subjects or others (see definitions, section 8.1).

If the report is supplied as a narrative, the minimum necessary information to be provided at the time of the initial report includes:

- Subject number
- A description of the event
- Date of onset
- Current status
- Whether study treatment was discontinued
- The reason why the event is classified as serious
- Investigator assessment of the association between the event and study treatment

### **8.3.1 Investigator reporting: notifying the medical monitor**

CONFIDENTIAL

Any study-related unanticipated problem posing risk of harm to subjects or others, and any type of serious adverse event, must be reported to the medical monitor (per Section 8.6) within 5 working days of the event. The investigator will keep a copy of this SAE report on file at the study site.

Significant new information on ongoing serious adverse events should be provided promptly to the medical monitor as follow-up reports.

### **8.3.2 Investigator reporting: notifying the Penn IRB**

This section describes the requirements for safety reporting by investigators who are Penn faculty, affiliated with a Penn research site, or otherwise responsible for safety reporting to the Penn IRB. The University of Pennsylvania IRB (Penn IRB) requires expedited reporting of those events related to study participation that are unforeseen and indicate that participants or others are at increased risk of harm. The Penn IRB will not acknowledge safety reports or bulk adverse event submissions that do not meet the criteria outlined below. The Penn IRB requires researchers to submit reports of the following problems within 10 working days from the time the investigator becomes aware of the event:

- Any adverse event (regardless of whether the event is serious or non-serious, on-site or off-site) that occurs any time during or after the research study, which in the opinion of the principal investigator is:

Unexpected (An event is “unexpected” when its specificity and severity are not accurately reflected in the protocol-related documents, such as the IRB-approved research protocol, any applicable investigator brochure, and the current IRB-approved informed consent document and other relevant sources of information, such as product labeling and package inserts.)

**AND**

Related to the research procedures (An event is “related to the research procedures” if in the opinion of the principal investigator or sponsor, the event was more likely than not to be caused by the research procedures.)

#### **Reporting Process**

Unanticipated problems posing risks to subjects or others as noted above will be reported to the Penn IRB using the form: “Unanticipated Problems Posing Risks to Subjects or Others Including Reportable Adverse Events” or as a written report of the event (including a description of the event with information regarding its fulfillment of the above criteria, follow-up/resolution and need for revision to consent form and/or other study documentation).

Copies of each report and documentation of IRB notification and receipt will be kept in the Clinical Investigator’s study file.

#### **Other Reportable events:**

For clinical drug trials, the following events are also reportable to the Penn IRB:

- Any adverse experience that, even without detailed analysis, represents a serious unexpected adverse event that is rare in the absence of drug exposure (such as agranulocytosis, hepatic necrosis, Stevens-Johnson syndrome).
- Any adverse event that would cause the sponsor to modify the investigators brochure, protocol or informed consent form, or would prompt other action by the IRB to assure protection of human subjects.
- Information that indicates a change to the risks or potential benefits of the research, in terms of severity or frequency. For example:
  - An interim analysis indicates that participants have a lower rate of response to treatment than initially expected.
  - Safety monitoring indicates that a particular side effect is more severe, or more frequent than initially expected.

CONFIDENTIAL

- A paper is published from another study that shows that an arm of your research study is of no therapeutic value.
- Change in FDA safety labeling or withdrawal from marketing of a drug, device, or biologic used in a research protocol.
- Breach of confidentiality
- Change to the protocol taken without prior IRB review to eliminate apparent immediate hazard to a research participant.
- Incarceration of a participant when the research was not previously approved under Subpart C and the investigator believes it is in the best interest of the subject to remain on the study.
- Complaint of a participant when the complaint indicates unexpected risks or the complaint cannot be resolved by the research team.
- Protocol violation (meaning an accidental or unintentional deviation from the IRB approved protocol) that in the opinion of the investigator placed one or more participants at increased risk, or affects the rights or welfare of subjects.

### **8.3.3 Investigator reporting: Adverse Event Reporting to ACC Data and Safety Monitoring Committee (DSMC)**

Common Toxicity Criteria: Toxicity will be evaluated with the NCI Common Toxicity Criteria (CTCAE) v. 4.0.

Serious Adverse Events (SAEs): SAE is defined as any of the following:

- Fatal or life-threatening (real risk of dying) event
- Requires or prolong hospitalization
- Causes persistent or significant disability/incapacity
- Results in a birth defect or congenital anomaly
- Causes cancer
- All hospitalizations or prolongation of existing hospitalization for medical events regardless of phase of study, expected or unexpected attributions are SAE's.

Serious, unexpected drug-related adverse events will be reported to the University of Pennsylvania IRB, and the University of Pennsylvania Cancer Center Data and Safety Monitoring Committee (DSMC) using the expedited reporting guidelines as is required by each board. Grade 3 or higher adverse events must be reported to the DSMC within 10 days of knowledge of the event. All unexpected deaths must be reported within 24 hours of knowledge of this event. All other deaths must be reported within 30 days of knowledge of this event. Adverse events that meet the DSMC reporting requirements will be entered into Velos with an e-mail alert (if applicable) to the DSMC.

### **8.3.4 Notifying the study sponsor**

Investigators must report serious adverse events (SAE) attributed to TACE or HCQ to the study sponsor within the timelines described below.

- Relevant follow-up information such as resolution and duration of the SAE attributed to TACE or HCQ should be submitted to the study sponsor as soon as it becomes available.

CONFIDENTIAL

This material is the property of the University of Pennsylvania. Do not disclose or use except as authorized in writing by the study sponsor

- Serious AE reports that are related to the TACE or HCQ and AEs of Special Interest (regardless of causality) will be transmitted to the study sponsor within 10 working days from the date investigators are made aware of the AE.
- Serious AE reports that are unrelated to the TACE or HCQ will be transmitted to the study sponsor within thirty (30) working days from the date investigators are made aware of the AE.
- AEs of Special interest are defined as AEs involving hepatotoxicity or renal toxicity occurring any time during the study period after initial TACE has been performed. These events are of special interest because they occur after therapies (i.e. HCQ and TACE) are first combined.
- All Non-serious Adverse Events originating from the study will be forwarded in an annual report to the study sponsor.

### **8.3.5 Sponsor reporting: Notifying FDA**

This study is IND exempt and reporting to the FDA is voluntary using the FDA's website for voluntary reporting.

### **8.4 Unblinding Procedures**

N/A

### **8.5 Stopping Rules**

The study will be terminated after completed follow up of the last patient enrolled (ie 6 months after this patient completes HCQ therapy). Alternatively, the protocol may be terminated prematurely for safety/toxicity issues as outlined in section 3.4 or for failure to demonstrate efficacy in stage one of the Phase II clinical design.

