$\geq 2$	Stop Dose Escalation 
 
• This dose exceeds the MTD
 
• Three additional patients will be entered at the next lowest dose level if only 3 patients were treated previously at that dose
 

1 out of 3	Enter 3 more patients at this dose level 
 
• If 0 of these 3 additional patients experience DLT, proceed with dose
 

CONFIDENTIAL

This material is the property of the University of Pennsylvania. Do not disclose or use except as authorized in writing by the study sponsor

	
escalation to the next level
 
 
• If 1 or more of these 3 additional patients experience DLT, then dose escalation is stopped. This dose level exceeds the MTD
 
• Three additional patients will be entered at the next lowest dose level if only 3 patients were treated previously at that level
 

≤1 out of 6 at the highest tolerable dose	This is considered the MTD. At least 6 patients must be enrolled at the MTD.

Table: Hydroxychloroquine Dose Escalation Schema

Dose level	HCQ
-1a	200 mg qday (9AM)
1	400 mg qday (9AM)
2	400 mg BID (9AM/9PM)
3	600 mg BID (9AM/9PM)

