### 3.4 Dose Reduction Schema

Toxicities will be evaluated using the Common Terminology Criteria of Adverse Events (CTCAE) version 4.0. Patients developing grade 3 or higher toxicity of any kind, which does not meet the definition of DLT, will call for holding HCQ therapy until the toxicity resolves to grade  $\leq 1$ . Any adverse effect attributed as possibly, probably or definitely related solely to HCQ will result in the dose being held until the adverse effect has resolved to  $\leq$  grade 1 or baseline. If the adverse effect resolves, reinstatement of treatment can occur but at a reduced dose as described below (HCQ Dose Reduction Schema). If the adverse effect recurs at the reduced dose, treatment will be held until the adverse effect has resolved to  $\leq$  grade 1 and when resolved treatment can be reinstated at the next lower dose level. No more than 2 dose reductions are allowed during the maintenance cycles.

Toxicities that may be attributable to HCQ include nausea, vomiting, diarrhea, rash, and visual field changes. If any of these adverse events occur at grade  $\leq 2$ , HCQ may be continued and the adverse event managed with supportive care. With particular regard to visual field deficits patients should be cautioned to report any visual symptoms, particularly difficulty seeing entire words or faces, intolerance to glare, decreased night vision, or loss of peripheral vision. These symptoms of peripheral retinal toxicity should prompt drug discontinuation and ophthalmologic evaluation.

Table: Hydroxychloroquine Dose Escalation Schema

Dose level	HCQ
-1a	200 mg qday (9AM)
1	400 mg qday (9AM)
2	400 mg BID (9AM/9PM)
3	600 mg BID (9AM/9PM)

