### **8.6 Medical Monitoring**

It is the responsibility of the Principal Investigator to oversee the safety of the study at his/her site. This safety monitoring will include careful assessment and appropriate reporting of adverse events as noted above, as well as the construction and implementation of a site data and safety-monitoring plan (see section 9 Auditing, Monitoring and Inspecting). Medical monitoring will include a regular assessment of the number and type of serious adverse events to occur within 1 month of the event. Escalation of the dosage of HCQ in the phase I portion of the trial cannot proceed prior to review of patient records for DLT by the medical monitor.

The monitor's findings will be reported independently to the ACC and DSMC. If findings from the monitor's review of AEs are considered unacceptable due to major deficiencies, representatives from the Department of Compliance and Monitoring will meet with the PI to discuss the findings of the visit and review corrective actions as mandated by the DSMC. If the deficiencies involve subject safety or serious regulatory violations, the ACC Director, DSMC Chair, and DSMC Director will meet to discuss necessary actions concerning study status.

The PI is given five business days to respond to these finding. An evaluation of the deficiencies will be re-evaluated upon receiving the PI's response. At this time, if the DSMC Chair and the Director do not find the response satisfactory, the IRB and OHR will be alerted of the actions taken by the ACC. The DSMC Director will update the IRB and OHR of the corrective actions being taken and progress being made.

Medical monitoring by an independent clinician [name], MD, Department of Medicine, Division of Hepatology will include a regular assessment of the number and type of serious adverse events on a periodic basis. [name] is a board certified gastroenterologist with a clinical and research focus in hepatocellular carcinoma. [name] practices at the Philadelphia VA Medical center and therefore will not be biased by prior clinical contact or relationship with potential study subjects. [name] will be reached at [[contact]](mailto:[contact]) or via telephone at [contact].

CONFIDENTIAL

This material is the property of the University of Pennsylvania. Do not disclose or use except as authorized in writing by the study sponsor

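### The toxicity stopping rule in section 8.5 points to section 3.4, which holds only patient-level actions, and the protocol text states no study-level toxicity criterion for the Phase II expansion

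*Combined protocol and SAP*

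**What the plan says.** Section 8.5 (Stopping Rules) gives two grounds for ending the study early. One is failed efficacy in stage one of Phase II. The other is toxicity: "the protocol may be terminated prematurely for safety/toxicity issues as outlined in section 3.4".

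Section 3.4 (Dose Reduction Schema) tells the investigator when to hold HCQ in a patient, when to restart at a lower dose, and when visual symptoms require stopping the drug. It adds a limit, "No more than 2 dose reductions are allowed during the maintenance cycles", and the table of dose levels.

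The cohort-level toxicity rules are in the 3+3 table of section 3.1. They end with the MTD defined as at most 1 DLT in 6 and the requirement that "At least 6 patients must be enrolled at the MTD". Section 8.6 adds a check by the medical monitor: "Escalation of the dosage of HCQ in the phase I portion of the trial cannot proceed prior to review of patient records for DLT".

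Phase II (section 7.1) treats 46 patients at the MTD, 6 of them from Phase I. It stops at 16 patients if there are 7 or fewer complete responses.

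**The concern.** A reader who follows section 8.5 to find out when toxicity ends or suspends the trial finds no answer in section 3.4. This matters most in the expansion. Most of the patients are treated there, and the Phase I rules no longer apply.

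Section 4.3 says that HCQ with TACE has not been tested in a clinical trial. The reassuring HCQ experience in section 1.5 comes from combinations with other anticancer agents. If toxicity at the declared MTD proved higher than six patients could show, the overseeing bodies would receive the events but would have no agreed point at which to pause accrual.

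A rule would also need a DLT count that is defined and ascertained in the same way for every patient. The current text does not ensure that.

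**Working it through.** **1. Is there a criterion elsewhere in the protocol?**

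| Section | What it provides | Study-level toxicity limit in Phase II? |
|---|---|---|
| 3.1, 3+3 table | Escalation and choice of MTD | No, Phase I only |
| 3.2 | DLT as a Phase I endpoint | No |
| 3.4 | Hold, reduce or stop HCQ in one patient | No |
| 7.1 | Look at 16 patients | No, complete responses only |
| 7.2 | DLT tables for Phase I; response, LPFS and OS for Phase II | No |
| 8.3.2 to 8.3.4 | Reporting to IRB, DSMC and sponsor | No count or rate |
| 8.6 | SAE review; DLT check before escalation | No count or rate |

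**2. What six patients show.** New patients in Phase II: 46 − 6 = 40 (10 in stage one, 30 in stage two). The exact 95% interval for the DLT rate is 0.4% to 64.1% after 1/6; after 0/6 its upper limit is 45.9%. The chance of passing is P(X ≤ 1 | n = 6, p) = (1−p)^6 + 6p(1−p)^5:
- p = 0.33: 0.090 + 0.267 = 0.358
- p = 0.40: 0.047 + 0.187 = 0.233

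These rates are scenarios chosen here; the documents give no expected or tolerable DLT rate.

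**3. The existing look.** P(X ≤ 7 | n = 16, CR 0.40) = 0.716, which reproduces the stated 72%. At CR 0.60 it is 0.142. Section 3.1 says that 12 patients are accrued in stage one, but its rule and section 7.1 use 16, so 16 is used here.

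**4. An illustrative limit: pause at k or more DLTs in 16, given at most 1 in the 6 Phase I patients.**

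P(pause) = [P(X6=0)·P(Y10≥k) + P(X6=1)·P(Y10≥k−1)] / P(X6≤1)

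For k = 5 and p = 0.40: (0.0467 × 0.3669 + 0.1866 × 0.6177) / 0.2333 = 0.568.

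| True DLT rate | k = 4 | k = 5 | k = 6 |
|---|---|---|---|
| 1/6 | 0.154 | 0.045 | 0.010 |
| 20% | 0.242 | 0.086 | 0.022 |
| 25% | 0.391 | 0.175 | 0.059 |
| 33% | 0.627 | 0.375 | 0.173 |
| 40% | 0.790 | 0.568 | 0.327 |

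**5. Effect on enrolment with k = 5.** This assumes that every pause becomes a stop and that DLT is independent of response. Expected new patients are 10 + 30 × (1 − P(futility stop)) × (1 − P(pause)).

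| True CR | No toxicity rule | DLT rate 33% | DLT rate 40% |
|---|---|---|---|
| 40% | 18.5 | 15.3 | 13.7 |
| 60% | 35.7 | 26.1 | 21.1 |

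Expected stage-two DLTs at CR 60%:
- 33%: 30 × 0.858 × 0.33 = 8.5, falling to 8.5 × 0.625 = 5.3
- 40%: 30 × 0.858 × 0.40 = 10.3, falling to 10.29 × 0.4324 = 4.45

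**6. The DLT window.** Section 3.2 leaves out the day after TACE; section 3.1 does not. Both sections name Week 12 as the end, and both also give an end 4 weeks (3.1) or 1 month (3.2) after the second TACE. For a second TACE at Week 8, 8 + 4 = 12 and the two agree. Section 6.8 gives some unilobar patients their second TACE at Week 10. Then 10 + 4 = 14, and the calendar end and the event-based end conflict.

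**7. Laboratory tests.** The unilobar timeline in section 3.1 promises the same laboratory schedule as for bilobar disease. Bilobar patients have tests at Week 10, two weeks after a Week 8 second TACE. For unilobar patients with a second TACE at Week 10, section 6.9 requires nothing at Week 12 and section 6.10 lists imaging and a visit, without laboratory tests, at Week 14. The next listed tests are at the 3-month visit (6.11). Bilirubin, transaminase, creatinine and INR events just after the second procedure could be missed. If 10% or 20% of DLTs went uncounted (assumption; the rate becomes p × 0.9 or p × 0.8), the k = 5 pause probability would fall from 0.568 to 0.458 or 0.347 at 40%, and from 0.375 to 0.287 or 0.206 at 33%.

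**The case against.** **Oversight.** A reader might infer that the expansion runs without safety oversight. The documents do not support that:
- Section 8.3.3: "Grade 3 or higher adverse events must be reported to the DSMC within 10 days of knowledge of the event".
- Section 8.3.2 makes it reportable to the IRB when "Safety monitoring indicates that a particular side effect is more severe, or more frequent than initially expected".
- Section 8.3.4 sends the sponsor "AEs involving hepatotoxicity or renal toxicity occurring any time during the study period after initial TACE has been performed" as events of special interest.
- Section 8.6 has an independent hepatologist review SAEs. Where deficiencies involve subject safety, the cancer center and DSMC leadership "will meet to discuss necessary actions concerning study status".

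Sections 8.6.1 and 10.1 also adopt institutional monitoring plans that are not supplied and may contain a limit. This objection stands, and it confines the point to the protocol text. It does not repair the pointer in 8.5.

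**Window and laboratory tests.** It is tempting to say that the DLT window closes two weeks after a Week 10 TACE, or that no blood is drawn then. Neither is established. The event-based end runs to about Week 14, so the defect is a conflict. The time-line charts are not visible in the text reviewed and may list the tests.

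**The illustrative limit.** The figure of 5 in 16 is not calibrated. Several DLT items need no attribution to HCQ, and TACE alone raises liver tests (section 1.1) and has an average hepatic failure rate of 7.5% (section 3.2). Entry allows AST to 121 and ALT to 189 IU/L, about three times the stated limits of normal (121/41 = 2.95; 189/63 = 3.0), while DLT begins above five times. A raw count could therefore pause the trial for effects of TACE. At k = 5 the rule also misses a 33% rate with probability 1 − 0.375 = 0.625. A single look covers only 10 of the 40 new patients. All of this stands and shapes the fix.

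**Conclusion.** The point holds for the protocol text. Section 8.5 refers to a study-level toxicity rule that section 3.4 does not contain, and no other section states one for up to 40 new patients in Phase II. That conclusion rests on reading the sections and needs no assumed rate. What is missing is a stated criterion; discretionary oversight is in place, and an institutional rule may exist outside the documents.

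Three related defects would affect any DLT count: the day after TACE is excluded in one definition only; the window has two ends for a Week 10 second TACE; and section 6 lists no laboratory tests soon after that procedure.

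The size depends on the unknown DLT rate. The pause probabilities assume at most 1 DLT in the 6 Phase I patients and independent patients with a common DLT rate. The enrolment savings also assume that each pause becomes a stop, so they are upper figures for a rule that only pauses. They are smaller if HCQ adds nothing (CR 40%), because futility then stops most trials anyway.

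**What to change.** - **Section 8.5:** correct the pointer. State a Phase II toxicity criterion, or cite the institutional rule if one exists, that pauses accrual for DSMC review.
- **Where it applies:** at the existing 16-patient look, once the patients have completed the DLT window, and then through the 30 stage-two patients. The sponsor sets the limits against the DLT rate expected from TACE alone and reports the pause probabilities for the whole rule. Five or more in 16 is only a starting illustration.
- **Section 7.2:** add a DLT table for Phase II.
- **Sections 3.1 and 3.2:** use one DLT definition, with the day after TACE either in or out, and a window ending 4 weeks after the last TACE, but not before Week 12 in patients who have only one.
- **Section 6:** list laboratory tests about two weeks after a Week 10 second TACE (Week 12).

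The cost is a few sentences, one table, and one routine blood draw in a subset of patients. At the illustrative limit, the chance of an unneeded pause is 4.5%, 8.6% or 17.5% if the true rate is 1/6, 20% or 25%, and a pause is reversible. The look may wait about 4 weeks beyond the response data for a unilobar patient without a second TACE (imaging at Week 8, window to Week 12). If accrual is not held at 16, about 3 to 6 more patients would enrol over 12 weeks at the planned 1 to 2 per month.
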